8.1.2 Adverse Reaction (AR)

An untoward medical occurrence which has a clear causal relationship between the event and the research procedure

8.1.3 Serious Adverse Event (SAE) / Serious Adverse Reaction (SAR)

Any untoward and unexpected medical occurrence or effect that:

- Results in death
- Is life-threatening – *refers to an event during which the subject was at risk of death at the time of the event; it does not refer to an event which hypothetically might have caused death if it were more severe*
- Requires hospitalisation, or prolongation of existing in-patients' hospitalisation
- Results in persistent or significant disability or incapacity
- Is or results in a congenital anomaly or birth defect

Medical judgement should be exercised in deciding whether an AE or AR is serious in other situations. Important AE/ARs which do not strictly meet the criteria for being serious but which may jeopardise the subject or require intervention to prevent one of the other outcomes listed in the definition above, should also be considered serious.

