8.1.4 Suspected Unexpected Serious Adverse Reaction (SUSAR)

Any adverse event which is classed as serious and for which there is evidence of a causal relationship with a research procedure, but where that event is unexpected.

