8.2.2 Serious adverse events/reactions

Any event which meets the criteria for an SAE should be discussed with the local principal investigator in the first instance. SAEs and SARs should be reported to the Sponsor within 24 hours of the local Principal Investigator (or nominee) becoming aware of the event, using the separate Sponsor-specific SAE form. Events listed in the expected events section below do not need to be reported as SAE/SARs, but will still be recorded as having met the criteria for being serious.

Events which are serious, causally related to a trial procedure (in the opinion of the PI), and which are unexpected (i.e. a SUSAR) should be reported to the Sponsor immediately upon the trial team becoming aware of the event. The Sponsor has a duty to undertake and co-ordinate the expedited reporting required following such events, including to the approving REC.

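### Protocol section 8.1.3 makes unexpectedness part of the SAE/SAR definition, which contradicts section 8.2.2 and makes the extra condition in 8.1.4 redundant for the listed outcomes

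*Protocol*

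**What the plan says.** Four parts of Protocol section 8 bear on this point.

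- **8.1.3 (SAE/SAR definition).** The opening line reads "Any untoward and unexpected medical occurrence or effect that", followed by the usual outcomes: death, threat to life, new or longer hospital stay, lasting disability, congenital anomaly. A closing paragraph adds a second route: "Medical judgement should be exercised in deciding whether an AE or AR is serious in other situations". That route has no expectedness condition.
- **8.1.4 (SUSAR definition).** "Any adverse event which is classed as serious and for which there is evidence of a causal relationship with a research procedure", with the further condition "but where that event is unexpected".
- **8.2.2 (reporting).** SAEs and SARs go to the sponsor within 24 hours and SUSARs immediately. There is one exemption: "Events listed in the expected events section below do not need to be reported as SAE/SARs". The same sentence adds that these events "will still be recorded as having met the criteria for being serious".
- **8.3 (expected events).** The list includes events that can carry a listed serious outcome. Examples are admission, disability or death caused by an underlying or earlier condition, and readmission or thoracic surgery caused by pleural infection or pneumonia. It also includes procedure-related events, such as bleeding, surgical emphysema and pneumothorax, each within stated limits.

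**The concern.** Seriousness describes the outcome of an event. Expectedness describes whether the event was foreseen. Sections 8.1.4 and 8.2.2 keep the two apart, while the opening line of 8.1.3 merges them. A site that classifies by the definition would not class an expected event with a serious outcome as an SAE or SAR. A site that follows the reporting section would record the same event as serious.

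What is at stake is the consistency of the serious-event classification across seven hospitals and 30 patients. With so few patients, a handful of events classified differently between sites would visibly change any count of serious events. Some of the affected events are procedural complications. The lay summary itself says thoracoscopy has a slightly higher complication risk than a standard drain, so these are events on which the arms could differ.

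**Working it through.** The protocol gives no figure for this point, so the check is a comparison of definitions.

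Notation: S = the event has one of the outcomes listed in 8.1.3; C = it is causally related to the research procedure; U = it is unexpected. I take U to mean not covered by the 8.3 list, because 8.1.3 does not define the word itself. The causal element of a SAR comes from 8.1.2, "An untoward medical occurrence which has a clear causal relationship between the event and the research procedure", which sets no expectedness condition.

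1. 8.1.3 as written: SAE = S and U; SAR = S and U and C.
2. 8.1.4: SUSAR = serious and C and U.
3. 8.2.2: an event that is S and not U is exempt from SAE/SAR reporting but counts as serious.

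For events with a listed outcome this gives:

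| Event | 8.1.3 as written | 8.2.2 and 8.1.4 | 8.1.3 without *and unexpected* |
|---|---|---|---|
| Unexpected, unrelated | SAE | Serious, reportable | SAE |
| Unexpected, related | SAR | Serious, SUSAR | SAR and SUSAR |
| Expected, unrelated | Not an SAE | Recorded as serious, exempt from reporting | SAE, exempt from reporting |
| Expected, related | Not a SAR | Recorded as serious, exempt from reporting | SAR but not SUSAR, exempt from reporting |

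Two results follow.

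- **Contradiction with 8.2.2.** In the two expected rows, 8.1.3 says the event does not qualify and 8.2.2 says it does. Under 8.1.3 the exemption would also have nothing to exempt.
- **Redundancy in 8.1.4.** Through the listed outcomes, S and U and C is already the SAR set, so adding U again separates nothing. The two sections do not contradict each other, but the condition in 8.1.4 does no work.

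With the two words removed, SAE = S, SAR = S and C, and SUSAR = S and C and U. All four rows then agree with 8.2.2 and 8.1.4.

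**The case against.** The strongest reply is that 8.2.2 is the operative instruction for exactly these events and says plainly that they are recorded as serious. Section 8.2.1 also has all adverse events and reactions recorded on the eCRF. This stands: the data are not shown to be lost, and the problem is inconsistent classification. It does not rescue the definition, because a site still has two rules that disagree.

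A reader might also infer more than the protocol supports.

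- **That every SAR is a SUSAR.** This holds only for events that qualify through the listed outcomes. The medical-judgement route in 8.1.3 has no expectedness condition, so a SAR reached that way may be expected.
- **That the wording of 8.1.3 is what makes the 24-hour and immediate routes overlap.** The 8.2.2 exemption has much the same effect. Even after the correction, a related serious event that must be reported is essentially one that is not on the expected list, and so a SUSAR.
- **That 3 to 6 deaths would drop out of the count.** This applies the background mortality of 10-20% in section 2.1.1 to 30 patients (0.10 × 30 = 3; 0.20 × 30 = 6). Section 5.3 excludes patients with short expected survival and those with sepsis needing more than basic fluid support, so the background rate need not apply. Section 8.3 lists death only where an underlying or earlier condition is the cause, and it is unclear whether death from the pleural infection itself is covered. Mortality at days 30 and 90 and surgical referral are secondary outcomes in section 4.3.2, captured whatever safety label they carry.
- **That the data monitoring committee would see an undercount by arm.** Sections 7.1.4 and 11.3 ask the committee to look at safety but specify no table of SAEs by arm and no restriction to events meeting 8.1.3.

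The Appendix 3 flow chart is missing from the text available here. It may show expectedness as a separate step, but that would not change the wording of 8.1.3.

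**Conclusion.** The point holds as an internal contradiction in an operative safety definition. Section 8.1.3 excludes expected events with a listed serious outcome from the SAE/SAR category, while 8.2.2 treats the same events as having met the seriousness criteria. As a lesser consequence, the unexpectedness condition in 8.1.4 is redundant for events with a listed outcome.

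The effect is that the set of events counted as serious depends on the section a site follows. The number affected cannot be derived from the protocol, which gives no rates for the 8.3 events in this selected population and no rule for tabulating SAEs. The feasibility primary outcome is not touched. The conclusion assumes that *unexpected* in 8.1.3 means not covered by section 8.3. It should be corrected, because the definition is wrong as written and the remedy is very small.

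**What to change.** Delete the two words *and unexpected* from the opening line of section 8.1.3. Keep expectedness only in 8.1.4, where it separates a SUSAR from other SARs, and in the reporting exemption of 8.2.2. Check that the Appendix 3 flow chart assesses seriousness before, and separately from, expectedness.

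The cost is a two-word amendment and a note to sites. Classification and tabulation of serious events become consistent. The 8.2.2 exemption from sponsor reporting for listed expected events is unchanged, so the deletion adds no reporting burden.

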8.1.4 Suspected Unexpected Serious Adverse Reaction (SUSAR)

Any adverse event which is classed as serious and for which there is evidence of a causal relationship with a research procedure, but where that event is unexpected.

8.2 RECORDING AND REPORTING PROCEDURES

Any questions concerning adverse event reporting should be directed to the trial manager or Chief Investigator in the first instance. A flow chart for adverse event recording and reporting can be found in Appendix 3.

8.2.1 All adverse events/reactions

An AE/AR should be recorded on the dedicated eCRF at the earliest opportunity following the trial team becoming aware of the event. This is most likely to be during the regular follow-up visits.

8.2.2 Serious adverse events/reactions

Any event which meets the criteria for an SAE should be discussed with the local principal investigator in the first instance. SAEs and SARs should be reported to the Sponsor within 24 hours of the local Principal Investigator (or nominee) becoming aware of the event, using the separate Sponsor-specific SAE form. Events listed in the expected events section below do not need to be reported as SAE/SARs, but will still be recorded as having met the criteria for being serious.

Events which are serious, causally related to a trial procedure (in the opinion of the PI), and which are unexpected (i.e. a SUSAR) should be reported to the Sponsor immediately upon the trial team becoming aware of the event. The Sponsor has a duty to undertake and co-ordinate the expedited reporting required following such events, including to the approving REC.

8.2.4 Following reporting

All reported events should be followed to resolution, with additional reports submitted as necessary. This should occur regardless of whether the patient was withdrawn from the trial as a result of the adverse event, unless the withdrawal request rescinded permission for outcome data to be collected and used.

8.3 EXPECTED ADVERSE EVENTS

The following are considered to be expected in the context of patients suffering with pleural infection and who require an intervention for fluid drainage.

- Chest pain, or discomfort around procedure site (unless not improving or remains unresponsive to analgesia)
- Bleeding associated with trial procedure (unless causing haemodynamic compromise, requiring transfusion, or requiring intervention to achieve haemostasis)
- Surgical emphysema (unless requiring surgical referral or causing airway compromise)
- Subcutaneous infection related to thoracoscopy or drain insertion, (unless unresponsive to antibiotic therapy)
- Chest drain falling out, becoming dislodged or becoming blocked
- Pneumothorax or evidence of non-expandable lung following chest drain insertion or thoracoscopy (unless requiring surgical intervention)
- Hospital admission, elective procedure or surgery, disability, incapacity or death due to underlying or pre-existing condition
- Delay in planned discharge date (unless due to a complication directly related to a trial procedure)
- Readmission to hospital or need for thoracic surgery due to pleural infection or pneumonia
- Hypotension or tachycardia due to sepsis requiring intravenous fluid support alone
- Hypothermia or hyperthermia due to sepsis, within the range $\geq 34.0^{\circ}\text{C}$ to $\leq 39.4^{\circ}\text{C}$
- A reaction to an administered medication (unless not described in the current version of the British National Formulary (BNF))

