6.3.2 Intervention arm

Patients who are allocated to the intervention arm should undergo a medical thoracoscopy on either the same or following day as they are *diagnosed as needing drainage*. Separate procedural consent must be taken as per local policy. Patients with a small effusion may have an induced pneumothorax performed prior to their thoracoscopy if necessary. The medical thoracoscopy should be performed as per local hospital guidelines, including using thoracic ultrasound where appropriate. Either a rigid or semi-rigid approach is acceptable, as are either single- or dual-port techniques. Conscious sedation may be used at the discretion of the operator. A sample of the pleural fluid which is drained should be sent as per section 6.4.2 below. During the procedure, the patient should undergo breakdown of accessible septations; parietal pleural biopsies; and intrapleural washout. Further details about these interventions may be found in the trial manual. At the end of the procedure, an appropriately-sized chest drain (minimum gauge 16 French) should be inserted and secured to the skin using at least one suture. The drain should be attached to an underwater seal (or digital equivalent) to allow full evacuation of the pleural cavity.

A post-procedure chest radiograph should be performed within 12 hours of completion of the thoracoscopy.

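### The expected-events list exempts any medication reaction described in the BNF from expedited SAE/SAR reporting, with no limit on severity or outcome

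*Protocol*

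**What the plan says.** Section 8.3 of the protocol lists events regarded as expected in this population. Its last entry is "A reaction to an administered medication (unless not described in the current version of the British National Formulary (BNF". Another entry on the list reads "Bleeding associated with trial procedure (unless causing haemodynamic compromise, requiring transfusion, or requiring intervention to achieve haemostasis".

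Section 8.2.2 sets out what listing does: "Events listed in the expected events section below do not need to be reported as SAE/SARs, but will still be recorded" as serious. The duty that is lifted is the one just before it: "SAEs and SARs should be reported to the Sponsor within 24 hours of the local Principal Investigator" or nominee becoming aware. The same section asks that any event meeting the SAE criteria be discussed first with the local PI.

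Immediate reporting applies to "Events which are serious, causally related to a trial procedure (in the opinion of the PI), and which are unexpected (i.e. a SUSAR"). Section 8.1.3 opens its definition of an SAE or SAR with "Any untoward and unexpected medical occurrence or effect that".

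On drugs, section 6.3.2 says of thoracoscopy: "Conscious sedation may be used at the discretion of the operator". Section 6.3.5 allows intrapleural enzymes in either arm at the treating physician's discretion.

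**The concern.** The entry's exception turns on whether a reaction is documented, not on how severe it is. The more familiar a drug hazard is, the more surely it is exempt, whatever its grade. A respiratory arrest under sedation or an anaphylactic reaction to an antibiotic, if the BNF describes it, is treated for Sponsor reporting like a mild rash.

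What is at stake is the speed and reach of oversight. Expedited reporting is the prompt route by which the Sponsor learns of a serious event at a site. The independent safety review is described as one look, placed after ten randomised patients in section 7.1.4 and after 15 enrolled in section 11.3. A fatal described reaction could thus wait for that review, or fall after it, without any Sponsor report having been required.

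**Working it through.** The protocol gives no figure to reproduce. The check is to follow one event through section 8: a life-threatening or fatal reaction to an administered drug, of a kind that the BNF describes.

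1. **Is it expected?** Yes, under the medication entry of 8.3. Neither seriousness nor outcome enters the test. The list's one mention of death concerns underlying or pre-existing conditions and does not restrict the medication entry.
2. **Is a 24-hour SAE/SAR report due?** No. Section 8.2.2 lifts that duty for listed events.
3. **Does the SAE/SAR definition bring it back?** No. Section 8.1.3 itself requires the event to be unexpected. Its medical-judgement clause can make an event serious but cannot make it unexpected.
4. **Does the SUSAR route bring it back?** No. Sections 8.1.4 and 8.2.2 both require the event to be unexpected.
5. **Must it be followed to resolution?** Section 8.2.4 places that duty on reported events. An event that need not be reported is outside it.
6. **What remains?** Discussion with the local PI, and an eCRF record flagged serious (8.2.2). Section 8.2.1 asks for entry at the earliest opportunity, sets no deadline, and expects this mostly to happen at regular follow-up visits. Case report forms at days 1, 3 and 7 would often capture an inpatient event early, but the protocol does not require anyone to alert the Sponsor.

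Next, the 12 entries of 8.3 by the kind of limit each carries:

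| Kind of limit | Entries | Count |
|---|---|---|
| Severity or response to treatment | chest pain, bleeding, surgical emphysema, subcutaneous infection, pneumothorax, hypotension or tachycardia, temperature | 7 |
| Cause only | admission, disability or death from an underlying condition; delayed discharge; readmission or surgery for pleural infection or pneumonia | 3 |
| None | drain dislodged or blocked | 1 |
| Documentation in the BNF | medication reaction | 1 |

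Check: 7 + 3 + 1 + 1 = 12. The cause-only entries concern the disease, other existing conditions or the discharge date. Among entries for harm from something done or given to the patient, the medication line and the drain line are the two without a severity limit. Of these, only the medication line readily extends to a fatal outcome.

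**Scope.** The entry covers any administered medication: sedatives, local anaesthetic, antibiotics and intrapleural enzymes. It applies in both arms.

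**The case against.** The strongest reply is that the event is not lost. The exemption sentence in 8.2.2 goes on to require that listed events be recorded as serious, the local PI is involved, and a death also counts in all-cause mortality at days 30 and 90 (section 4.3.2). This stands, and it limits the point to oversight.

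A second reply is that the exemption was deliberate. The trial is a non-CTIMP with no investigational medicine, Appendix 6 shows that medication reactions were added to the list by a substantial amendment, and the list applies no uniform severity rule. This also stands in part. Exempting known reactions to routine drugs is a reasonable choice, but it does not explain why severity is ignored here when seven other entries limit it.

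A third reply is that the word described could be read to cover severity as well as type. That reading is possible. The text does not say so, and sites could apply it differently.

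A reader might also infer two stronger points, which the documents do not support:

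- **Bias between arms.** Sedation is named for thoracoscopy and not in the control-arm section, and with 30/2 = 15 patients per arm one unreported event is 1/15 = 6.7 percentage points. But that figure concerns a tally of Sponsor forms, which no outcome or analysis in the protocol uses. The seriousness record covers both arms, sedation is discretionary, silence in section 6.3.1 does not show that controls receive none, and the entry covers every drug in either arm.
- **A list that contradicts itself.** A bleed needing transfusion after enzyme therapy might seem reportable under the bleeding line and exempt under the medication line. The bleeding line is limited to bleeding linked to the trial procedure, and enzyme therapy is discretionary later treatment, so a direct conflict is not established. It remains true that nothing says which line governs when two apply.

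**Conclusion.** The gap is real on the text of section 8. A described medication reaction of any severity, including a fatal one, is exempt from the 24-hour report, cannot be a SUSAR, and is outside the follow-to-resolution duty. The loss is prompt Sponsor oversight; the data are kept. No distortion of a trial result is shown, and no number can be put on how often the exemption would apply.

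The conclusion rests on two assumptions. The BNF is not at hand, so whether it describes a given reaction is assumed; the exemption applies wherever it does. The Appendix 3 flow chart is not shown, so a restriction there cannot be ruled out, although the section 8 text contains none. This is an inexpensive improvement to safety reporting, not a flaw in the trial's inference.

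**What to change.** Add a limit to the medication line of 8.3 in the protocol's own seriousness terms, for example: *unless fatal, life-threatening, resulting in persistent or significant disability, or not described in the BNF*. A described reaction whose only serious feature is a longer admission would then stay exempt, which keeps the burden low. Add one sentence to 8.3 saying that where two lines apply to one event, the stricter governs. Check that the Appendix 3 flow chart agrees.

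One consequence should be accepted knowingly. A severe reaction taken off the list becomes unexpected, so if the PI judges it related to a trial procedure it follows the SUSAR route, as a bleed above the limit of the bleeding line already does. The alternative is to disapply the 8.2.2 exemption for fatal or life-threatening events related to a trial procedure. That would also require removing the word unexpected from the SAE/SAR definition in 8.1.3.

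The change affects reporting only, not treatment. Its cost is a short amendment and probably a few extra SAE forms among 30 patients.

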9. REGULATORY ISSUES

9.1 RESEARCH GOVERNANCE

This study will be conducted in accordance with:

- The International conference for harmonisation of good clinical practice (ICH GCP)
- The Research governance framework for health and social care, and
- The Declaration of Helsinki

9.2 ETHICS APPROVAL

A research ethics committee will review the trial prior to recruitment commencing. The REC will be asked to approve the trial protocol, GP letter, as well as all “public-facing” or “participant-facing” documentation (e.g. patient information sheet, consent forms, or advertising materials). They will also approve the questions to be asked during the semi-structured interview component of the study. All of the above will also be approved by the Sponsor.

